a) M-mode and 2-D echocardiography: The M-mode and 2-D echocardiograms will be used to provide indices of systolic and diastolic function, chamber size (LV, RV, LA and RA) and left ventricular wall thickness. Only good quality echoes (see appendix C) will be accepted. The first 5 echoes will be submitted to the SOLVD echo core laboratory for analysis and all 5 echoes should be analyzable for all key variables. Deficiencies will be immediately notified to the participating clinics. All echocardiograms will be recorded on SOLVD Registry videotape which will be transmitted to the core laboratory for central analysis. See appendix C for further details.

b) Physical examination and history. In all patients, the clinical data on the baseline form will be collected again. This will provide a comparison of the data extracted from the patient's charts versus a direct, more standardized data collection.

c) Baseline plasma renin and cathecholamine: After the insertion of an indwelling venous cannula and with the patient resting for 30 minutes in the supine position, a 20 ml sample of blood will be drawn for plasma renin and catecholamines. The blood samples will be frozen at -70 degrees centigrade and shipped in batches to the core laboratory at the University of Texas, Galveston. See appendix C for details.

d) Seventy-minute ambulatory monitoring. All patients will receive a one-hour ten-minute ambulatory monitoring while the patient is in the outpatient clinic. The period will include the 6-minute walking test. The tape will be analyzed at a central facility. Data from BHAT (Davis et al. 1986) indicate that a one-hour ambulatory monitoring may be as predictive of mortality and sudden death as 24-hour monitoring. This seems especially likely in a group of patients with a high prevalence of arrhythmias as expected in this Registry. Coupled with the convenience and low cost, a one-hour ambulatory monitoring may be a reasonable estimate of ventricular arrhythmia. See appendix C for details.

e) Six minute walking test. The distance walked in six minutes has been shown to be a reasonable assessment of the functional capacity of patients with congestive heart failure (Guyatt et al. 1985). Previous studies have shown a good correlation between the 6-minute walking test and symptoms and objective measures of functional capacity such as VO2max. See appendix C for procedures for conducting this test.

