trials, copy Eligibility ID:	26.4 Myocardial infarction within 30 days of expected randomization	Y	N	U
	26.5 History of intolerance to . enalapril	Y	N	U
25.2 If participant has been randomized into the SOLVD trials, copy Randomization ID:	26.6 Currently taking ACE inhibitor and unwilling/unable to discontinue	I Y	N	U
	26.7 Renal failure	Y	N	U
(If participant randomized, SKIP to Q. 27) Yes No Unrecorded	26.8 Uncontrolled hypertension	Y	N	U
	26.9 Cor Pulmonale	Y	N	U
26. If participant was considered for but excluded from the SOLVD trials, please	26.10 Advanced pulmonary disease	Y	N	υ
	26.11 Major neurological disease	Y	N	U
26.1 Hemodynamically significant valvular or outflow tract obstruction Y N U	26.12 Cerebrovascular disease	Y	N	U
26.2 Constrictive pericarditis Y N U	26.13 Collagen vascular disease	Y	N	U

Т

SOLVD MAIN REGISTRY BASELINE FORM (screen 9 of 15) (RBF page 5 of 8)

		Yes	No	Unrecorded		Yes	No	Unrec
26.14	Any major cardiac surgery likely	¥	N	U	at an evented electificant month			
26.15	Unstable angina pectoris	Y	N	U	26.23 Suspected significant renal artery stenosis	Y	N	U
26.16	Cancer	¥	N	U	26.24 Woman likely to bear children	Y	N	U
	Immunosuppressive therapy			U	26.25 Other investigational drug pro- tocols (except compassionate use)	Y	N	U
	Active myocarditis Significant primary liver			U	26.26 Failure to give consent for the SOLVD trials	Y	N	U
26.20	disease Likely to be nonadherent (alco-	Y	N	U	26.27 Lack of adherence or tolerance to medication	Y	N	U
	holism, drug addiction, lack of a fixed address, etc.)	¥	N	υ	26.28 Lack of adherence to placebo run-in	Y	N	U
26.21	Syncopal episodes presumed to be due to life-threatening arrhythmian	6 Y	N	υ				
26.22	Other life-threatening disease or not realistically expected							
	to be discharged alive	Y	N	U				

				1			20	
27. For which trial is/was the parts		nt be	ing			Yes	No	Unreco
				28.10	Peripheral vascular disease	Y	N	υ,
Prevention Treatment Not considered/randomized	1			28.11	Edema	¥	N	U
		•		28.12	Breathlessness on exertion	Y	N	U
G. CLINICAL HISTORY 28.1 Date history taken (within 3 month)			Unrecorded rollment)	28.13	Asthma (If NO or UNRECORDED, skip to Q		N 15)	U
Month Day Year			.*	28.14	Approximate duration of asthma (in years):			]
28.2 Diabetes mellitus	¥	N	U	28.15	Pulmonary edema	Y	N	U
28.3 Chron. obstructive pulm. dis	¥	N	U	29.1	Previous myocardial infarction? (If NO or UNRECORDED, skip to Q		N	U
28.4 Cerebrovascular accident	Y	N	υ		Enter date of most recent myoca			

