28.5 Angina pectoris	¥	N	U	29.2	Enter date of most recent myoca	TUIAI		arce101
28.6 Peripheral embolism	Y	N	U		Month Year			
28.7 Pulmonary embolism	¥	N	U	29.3	Was the MI complicated by pulmo	narv	edem	۵.
28.8 Syncope	¥	N	U		shock, or heart failure?	Y	N	, n
28.9 Hypertension	Y	N	U					

SOLVD MAIN REGISTRY BASELINE FORM (screen 11 of 15) (RBF page 6 of 8)

٠

----

. .... . . .**...** 

30.	Smoking history	Yes	No	Unrecorded	Yes No Unreco
30.1	Has the participant ever been a smoker (tobacco)? (If NO or UNRECORDED, skip to Q.	¥ 31)	N	U	32. Permanent pacemaker? Y N U
30.2	Does the participant currently smoke?		N	U	33. Use of automatic implantable defibrillator? Y N U
31.	Alcohol consumption history	•	M	U I	34.1 Previous cardiac surgery, PTCA, or balloon valvuloplasty? Y N U (If NO or UNRECORDED, skip to Q. 35)
31.1	Has the participant ever regular consumed alcohol? (If NO, skip to Q. 32)		N	U	34.2 Enter date of most recent cardiac surgery, PTCA, or balloon valvuloplasty:
31.2	Is there history of alcohol abuse? (See Manual of Operations for guidelines)		N	υ	Month Year
31.3	Does the participant currently consume alcohol?	Y	N	υ	

ł

- -

	Type of cardiac surgery:	Yes	No	Unre	corded			2	les	No
34.3	Coronary artery bypass graft	¥	N	U	ſ		36.2	Potassium-sparing diuretic	Y	N
34.4	Valve replacement - aortic	¥	N	U	l			Antiarrhythmic drug other than bet blocker or calcium antagonist	ra- Y	N
34.5	Valve replacement - mitral	Y	N	U			36.4	Regular use of antiplatelet	Y	N
34.6	Percutaneous transluminal coronary angioplasty (PTCA)	Y	N	U	1		36.5	Beta-blocker	Y	N
34.7	Balloon walwuloplasty	Y	N	U	I		36.6	Long-acting oral nitrate or paste	Y	N
34.8	Other	Y	N	U	I		36.7	Hydralazine	Y	N
34.9	(If NO or UNKNOWN, skip to Q. 35 Specify:	·)			-		36.8	Open-label ACE inhibitor (Select "S" if in SOLVD trial)	Y	N
	EDICATIONS IN USE AT LAST HOSPITA	LI-		Yes	No		36.9	Digitalis	Y	N
	ATION OR OUT-PATIENT VISIT				••		36.10	Calcium antagonist	Y	N
35. I	Date of last hospitalization or ou	it-pat 7	ien	t vis	it:		36.11	Other vasodilator	Y	N
							36.12	Antihypertensive (other than above	e) Y	N
	Month Day Year						(conti	inued)		
36.1	Potassium-losing diuretic	Y	N							
	SOLVD MAIN REGISTRY BASELINE FORM (screen 13 of 15) (RBF page 7 of 8)									
		v.	-	No		T				

	Yes	No	
36.13	Other inotropic agent Y	м	39. Height (enter inches or cm):
36.14	Anticoagulant Y	N	39.1 in.
36.15	Insulin Y	N · .	
36.16	Steroids Y	N	39.2 cm.
36.17	Beta-2 agonist inhalers Y	N	beats/

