## SOLVD MAIN REGISTRY BASELINE FORM (screen 15 of 15) (RBF page 8 of 8)

SOLVD REGISTRY SUBSTUDY BASELINE FORM (screen 1 of 12) (RSB page 1 of 7)

A. IDENTIFYING INFORMATION	B. ECHOCARDIOGRAPHY ELIGIBILITY	Yes
<pre>1.1 Today's date:///</pre>	
 
3.1 Date 2D and M-mode echos done:
 
Month / Day / Year
 
3.2 Were these echocardiograms of good quality? (See protocol for criteria) (If NO, exit form)
 
3.3 Was Doppler echo done? (only for those participants in the Echo Substudy) (If NO, skip to Section C)
 
	Y Y
2.2 Participant's First Name: 2.3 Participant's Middle Initial:	3.4 Date Doppler done: /// Month Day Year	1

Т

c.	ETIOLOGY OF DISEASE AND NYHA CLASS			Yes
4.1	Indicate the primary etiology of the patient's heart disease (choose only ONE of the following):	5.	Indicate all of the following etiologies the have occurred (including the etiology specia bove):	nat ified
	Ischemic heart disease (HD) 1	5.1	Ischemic heart disease (IHD)	Y
	Hypertensive heart disease (HHD) 2	5.2	Hypertensive heart disease (HHD)	Y
	Active myocarditis 3	5.3	Active syocarditis	Y
	Valvular heart disease - aortic 4	5.4	Valvular heart disease - aortic	Y
	Valvular heart disease - mitral 5	5.5	Valvular heart disease - mitral	Y
	Idiopathic cardiomyopathy (specifics unknown) 6	5.6	Idiopathic cardiogyopathy (specifics unknown)	Y
	Specific cardiosyopathy (ax: viral, toxic, ETOH, postpartum, history of cocaine use) 7 (If none, skip to Q. 5)	5.7	Specific cardiomyopathy (ex: viral, toxic, ETOH, postpartum, history of cocaine use) (If NO, skip to Q. 6)	Y
4.2	Specify:	5.8	Specify:	
		6.	New York Heart Association CHF Class: (Choose only one)	

SOLVD REGISTRY SUBSTUDY BASELINE FORM (screen 3 of 12) (RSE page 2 of 7)

Contractor					
		Yes	No		Yes
D.	PAST CLINICAL HISTORY (up to completion			7.9 Hypertension	¥
	of the Registry Baseline form)			7.10 Peripheral vascular disease	Y
7.	Does the participant have a history of:		(restaut)	7.11 Edema	Y
7.1	Pulmonary edema	Y	М	7.12 Breathlessness on exertion	Y
7.2	Diabetes mellitus	Y	M	7.13 Asthma	¥
7.3	Chronic obstructive pulmonary disease	Y	N	(If NO, skip to Q. 8)	
7.4	Cerebrovascular accident	¥	N	7.14 Approximate duration of asthma:	] :
7.5	Angina pectoris	T	M	8. Cigarette smoking (ignore any other tobac	
7.6	Peripheral embolism	¥	M	8. Cigarette smoking (ignore any sther total 8.1 Has the participant ever smoked cigarette	
7.7	Pulmonary embolism	¥	N	regularly? (If NO, skip to Q. 9)	Y
7.8	Syncope	T	N		

•

•

т

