8.2	At what age did the participant first begin to smoke cigarettes regularly?	Yes
	years of age	8.7 - After 24 years of age cigts/we
8.3	For how many years in total has the participant smoked regularly?	8.8 - During last 6 months cigts/we
	years	8.9 Did the participant smoke any cigarettes in the past week?
8.4	For how many of those years did the participant smoke filter-tipped cigarettes?	9. Alcohol consumption history
	What (approximately) was the largest number of	9.1 Has the participant ever consumed alcohol regularly?
	cigarettes the participant generally used to smoke in a week? (Count 1 oz of handrolled to- bacco as 28 cigarettes) -	9.2 Does the participant currently consume alcohol regularly?
8.5	- Before 20 years of age cigts/week	9.3 Last week, how many drinks did the participant have? (1 drink = 12 oz beer = 4-5 oz wine =
8.6	- From 20-24 years of age cigts/week	1.5 oz spirits) drinks

.

,

SOLVD REGISTRY SUBSTUDY BASELINE FORM (screen 5 of 12) (RSE page 3 of 7)

9.4	Specify current drinking pattern: Heavy H Regularly R Socially S Rarely X Unknown U GO TO Q.10.1		Yes No Unk Previous myocardial infarction? Y N (If NO, skip to Q. 11) Date of most recent myocardial infarction:
9. 5	Number of days a weak the participant used to drink:	10.3	Month Year Was the MI complicated by pulmonary edema, shock, or heart failure? Y N
9.6	Number of drinks the participant used to consume per week (1 drink = 12 oz beer = 4-5 oz wine = 1.5 oz spirits):	11. 12. 13.1	Permanent pacemaker? Y N Use of automatic implantable defibrillator? Y N Previous cardiac surgery, PTCA, or
9 .7	Specify former drinking pattern: Heavy N Regularly R Socially S Rarely X Unknown U		balloon valvuloplasty? Y N (If NO, skip to Section E)

SOLVD REGISTRY SUBSTUDY BASELINE (screen 6 of 12) (RSB page 4 of 7)

.

Yes	No	Unknown	E.	MEDICATIONS CURRENTLY USED	Yes
13.2 Date of most recent cardiac surgery, PTCA,			15.1	Digitalis	Y
or balloon valvuloplasty:			15.2	Other instropic agent	Y
	s		15.3	Potassium-losing diuretc	Y
Month Year			15.4	Potassium-sparing diuretic	Y
14. Type of cardiac surgery:	1004012-00		15.5	Antiarrhythmic drug other than	v
14.1 Coronary artery bypass graft Y	N	U		beta-blocker or calcium antagonist	•
14.2 Valve replacement - aortic Y	N	υ	15.6	Regular use of antiplatelet	Y
14.3 Valve replacement - mitral Y	N	υ	15.7	Beta-blocker	Y
14.4 Percutaneous transluminal coronary	~	U	15.8	Long-acting oral nitrate and paste	Y .
angioplasty (PTCA) Y	N	U	15.9	Hydralazine	. Y

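### The Substudy form asks about regular cigarette smoking where the baseline form asks about any tobacco, so the smoking comparison promised in Section VII.b cannot be made like for like; alcohol has smaller gaps

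*Protocol*

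**What the plan says.** Section VII.b of the Protocol, on the Substudy history and examination, states: "In all patients, the clinical data on the baseline form will be collected again". It gives the reason: "This will provide a comparison of the data extracted from the patient's charts versus a direct, more standardized data collection".

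Smoking and alcohol are items 30 and 31 of the Registry Baseline Form (RBF), in the section headed "G. CLINICAL HISTORY", so they belong to the data to be collected again. The RBF asks "Has the participant ever been a smoker (tobacco" (item 30.1), then about current smoking (30.2). On alcohol it asks about ever-regular use (31.1), history of abuse (31.2) and current use: "Does the participant currently consume alcohol" (31.3).

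The Registry Substudy Baseline form (RSB) opens its smoking block with "8. Cigarette smoking (ignore any other tobac". Item 8.1 begins "8.1 Has the participant ever smoked cigarette" and goes on to require regular use; a NO sends the nurse to item 9. The nearest item on current smoking is 8.9, any cigarettes in the past week. On alcohol, 9.1 asks about ever-regular use, and 9.2 asks "Does the participant currently consume alcohol regularly".

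**The concern.** A comparison of chart with direct collection measures chart quality only if both sources answer the same question. Where the second question is narrower, a patient can be recorded correctly on both forms and still disagree. The disagreement then reflects wording, but looks like a charting error. Because the second definition lies inside the first, the artefact also has a direction: charts would appear to overstate exposure.

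At stake is the agreement estimate for ever and current smoking and, to a lesser degree, for current alcohol use. Direct confirmation of charted alcohol abuse is also missing. That item bears on alcoholic cardiomyopathy, which Section VI informally puts at 7-10% of patients.

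**Working it through.** The plan states no agreement figure, so there is none to reproduce. The check is an item-by-item comparison, followed by an illustration of size.

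**Step 1: the items side by side**

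| Topic | RBF | RSB | Same question? |
|---|---|---|---|
| Ever smoked | 30.1: any tobacco, no regularity threshold | 8.1: cigarettes, regular use | No |
| Currently smoke | 30.2: not limited to cigarettes | 8.9: cigarettes in past week; skipped if 8.1 = N | No |
| Ever-regular alcohol | 31.1 | 9.1 | Yes |
| Alcohol abuse | 31.2 | none | No direct counterpart |
| Current alcohol | 31.3: any use | 9.2: regular use | No |

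**Step 2: follow patients with perfect charts through both forms**

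- *Has only ever smoked a pipe or cigars:* 30.1 = Y; 8.1 = N; items 8.2-8.9 are skipped. If the patient still smokes, 30.2 = Y and the RSB has no answer to set against it.
- *Former regular drinker who now drinks occasionally:* 31.1 = Y and 9.1 = Y, which agree; 31.3 = Y but 9.2 = N.
- *Occasional drinker who never drank regularly:* 31.1 = N, and the RBF then skips to item 32, so 31.3 is never answered. This patient creates no mismatch.

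**Step 3: direction**

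Everyone who ever smoked cigarettes regularly has been a tobacco smoker, and everyone who now drinks regularly now drinks. For 30.1 v 8.1 and 31.3 v 9.2, wording alone can therefore produce only chart Y / Substudy N, never the reverse.

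**Step 4: size for ever-smoking, on assumed prevalences**

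The Substudy size, 1000, comes from Section VII. The documents do not give the other two inputs, so they are varied: p, the share who ever smoked cigarettes regularly (0.5 to 0.7), and b, the share who are Y on 30.1 but N on 8.1 (0.02 to 0.10). With perfect charts:

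- observed agreement Po = 1 - b
- chance agreement Pe = (p + b)p + (1 - p - b)(1 - p)
- kappa = (Po - Pe)/(1 - Pe)
- discrepant patients = 1000b

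Worked case, p = 0.7 and b = 0.10: Po = 0.90; Pe = 0.80 × 0.70 + 0.20 × 0.30 = 0.62; kappa = 0.28/0.38 = 0.74.

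| b | Discrepant of 1000 | Agreement | Kappa, p = 0.5 | p = 0.6 | p = 0.7 |
|---|---|---|---|---|---|
| 0.02 | 20 | 98% | 0.96 | 0.96 | 0.95 |
| 0.05 | 50 | 95% | 0.90 | 0.89 | 0.87-0.88 |
| 0.10 | 100 | 90% | 0.80 | 0.78 | 0.74 |

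With identical wording, b = 0, and kappa would be 1 in every cell. The remaining disagreement would be true chart error plus real change before the Substudy visit, which may be up to 90 days after enrollment.

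**The case against.** The strongest reply is that the Protocol promises a comparison but names no item pairs, agreement statistic or definition of chart error. These may be left to an analysis plan, and an analyst who sees that 8.1 is limited to cigarettes need not pair it with 30.1. This stands as far as it goes: the documents do not say that such patients will be scored as discrepant. But declining the pairing does not rescue the comparison. Tobacco other than cigarettes is recorded nowhere on the RSB, so the choice is between comparing unlike items and omitting smoking from what Section VII.b promises.

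A reader might infer that the alcohol questions are mismatched throughout. They are not. Items 31.1 and 9.1 agree, and the current-use gap is confined to former regular drinkers who now drink occasionally. Even these may be recoverable: 9.3 asks for drinks in the last week, and 9.4 offers social and rare drinking as current patterns. Whether 9.2 = N bypasses those items cannot be read in the text at hand.

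A reader might also infer that alcohol abuse cannot be checked at all. The RSB holds indirect evidence: the heavy category in 9.4 and 9.7, former drinks per week in 9.6, and etiology items that list alcohol as a specific cardiomyopathy. None of these is the RBF question, which refers to guidelines in a Manual of Operations that is not shown.

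The size is open to challenge too. An irregular cigarette user may not be called a smoker on 30.1, which would leave mainly pipe and cigar smokers and favour the low end of the range. Real charts also omit smoking, so observed discrepancies need not all run one way; only the wording effect does.

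Finally, chart validation is not among the aims in Section II, and Section X does not name smoking or alcohol among its example covariates. This limits the consequence but does not remove the mismatch.

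**Conclusion.** The point holds as a minor defect in the forms, and chiefly for smoking. As written, the RBF and RSB do not permit a like-for-like comparison of ever or current smoking, and the RSB holds nothing that would correct it. Current alcohol use has a smaller and possibly recoverable gap, and history of alcohol abuse lacks a direct counterpart.

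The 20-100 discrepancies, and kappa of about 0.95 down to 0.74, apply to ever-smoking only. They rest on three assumptions: the nearest items are paired, charts are perfect, and 2-10% of 1000 patients are affected. No comparable figure can be given for alcohol.

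The documents do not support a wider conclusion that the whole chart comparison is unsound. Most other history items match, including the 28.x and 7.x lists, previous infarction, pacemaker and cardiac surgery. The primary outcome, all-cause mortality, is unaffected.

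**What to change.** Add RBF items 30.1, 30.2, 31.2 and 31.3 to the RSB word for word, with the RBF skip rules. Put the two smoking items ahead of 8.1, so that its skip cannot bypass them. Use these four, together with the existing 9.1, for the chart-versus-direct comparison of smoking and alcohol. Keep the detailed cigarette and drinking items as additional data outside that comparison.

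The cost is four extra Yes/No questions per Substudy patient, under a minute each visit, and a small revision of the form and its data-entry screens. Nothing already collected is lost.

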# REGISTRY DEATH CERTIFICATE COVER SHEET

VERSION A / 3-18-86	· ·
RE+ 13:	VISIT: FINE: RDC
INSTRUCTIONS: Cooplete and attach this fore to the Send both to the SOLVD Coordinating C	participant's Death Certificate. Center in Chapel Hill, MC.
BEATH CERTIF	ICATE COVER SHEET
A. IDENTIFYING INFORMATION	4. Was this a hespitalized docth?
1. Today's Bate:/ / / / Year	
2.1. Last Neer:	S. Cause of Death:
2.2. First Nee:	L Has an autopsy performed?
2.3. Riddle Meet	No N
2. Bate of Besth:	9. INITIAL OF PERSON COMPLETING THIS FORM 7. Initials
	•

hey

•

;

R	EGISTRY		
DESIGNAT	TION OF DEATH F	OR.	λ
VERSIO			
following a contract participant's cardiovascular or moncardiovascular. Print clearly when entering a respon questions, circle the one appropriat	en all clinical information has been collected death to determine the cause of death as use in the appropriate boxes. For aultiple choice e letter or muscer corresponding to the response various questions are enclosed in boxes directly energial destructions for Completing Fores for		
DESIGNATION OF DEATH 1	TORM (screen 1 of 4 ) (RDD page 1 of 3 )		
A. IIEKTIFYING INFORMATION	B. TYPE DF MEATH Condition of Beath:		
1. Today's Bate:////	4.1. Buring a hospital addission	Yes	
2. Bate of Beath:/Bay /	If Yes, conclete the REGISTAY NOSFITALIZATION FOPM.		
2.1. Tier of Booth: a) 2	4.2. Mart ved	۲	
3) 3.8 A	4.3. Trausetic	¥	
Polle seeses P	4.4. Suitife	Ÿ	
3.1. Lest Name:			
3.2. First Neer:			
		:	
3.3. Niddle Hone:	1		

ź.

. DESIGNATION OF DEATH P	ERR (SETDER 2 ST 4 ) (LOD page 2 ST 3 )
Condition of Beath: Yes No	6.1. If Cardiovascular (C). indicate one type
4.5. Within 7 days of	Cardiac C
a syscardial infarction	Strate 5
4.4. Hithin 7 days of	Pulsonary estalisa V
Cardiac surgery	Sther wascular
4.7. Mithin 7 days of	sr gatmen D
A.1. MITHIN / GAN A. MMR-CETEISC SHIBELY	
C. CAUSE OF DEATH	If Stroke (S) or Pulsonary embolise (V) or Other vascular or unknown (O). go to section D. INITIALS OF PERSON COMPLETING THIS FORM, Swestion S. on page 3.
5. Cause of SouthCardiowascular C	
Hencardiavaacular H	4.
If Moncardiavascular (N), go ta Suestion 7.1, on page 3.	
- BESIGNATION OF BEATH	FORM (screen 3 of 4 ) (NDD page 2 of 3 )
(Cardiar Beath)	6.3. If Other (D), specify:
4.2. Choose the one aost litely terminal eventments.	PLEASE PRINT ELEAPLY.
Circle ang mumber.	
Probable prrhytheis without preceding worsening symptods of CiF	
Prebable arrhytheis with some proceding cersening symptoms of LP 2	•
Primarily related to pump failure (even if terainel event was an arrhythela)	
Sther	

r

2

• •

So to section D. THITTALS OF PERSON TRELETING THIS FORM Auestion 8. on page 3.

-

Other .....

:

• 1 If the number circled was 1, 2 or 3, 90 is section D. INITIALS OF PERSON CORLINE THIS FORM, Buestion B. on page 3.

7.1. If Noncardiovascular (N), indicate the type of death	7.2. If a privery event, mas death due to cancer?
Circle and maker. A secondary complication of beart failure (e.g., proconid, bepatic or renal dysfunction, StC.)	No N If No, go to Guestian 8. 7.3. If Yes (cancer), specify primary site:
Meither 1 or 2	Go to Buestion 8. 7.4. If Meither 1 or 2 (3), specify:
If meither 1 or 2 (3), go to Buestion 7.4.	B. INITIALS OF PERSON COMPLETING THIS FORM B. Initials

;

# Appendix C PROTOCOLS FOR SUBSTUDY PROCEDURES

### I. Collection and Shipping of Blood Samples for Catecholamine and Renin

The following tubes will be provided in dry ice by the central laboratory with each shimpent to the clinical centers. Please retain the insulated box for returning the samples in dry ice.

- (a) White top Collection tube for plasma catecholamines.
- (b) Lavender top Collection tube for renin samples.
- (c) Red top Storage tube for plasma catecholamines (store the separated plasma in these tubes).
- (d) Blue top Storage tube for renin samples.
- (e) Black top Quality control reference for plasma tubes for catecholamine storage. Keep this in -70°C with your samples.
- Collection of Blood Samples:

When the study patient is at the stage for blood drawing, a 21 gauge butterfly needle will be placed in a suitable vein and is flushed with heparinized saline. The patient now rests supine quietly for 30 minutes. Use LAVENDER TOP tubes (vacutainer B-D) for collecting samples for renin assay. Use the WHITE TOP tube for collecting the samples for catecholamine assay. Prechill these tubes in ice (4°C). Then a 20 ml sample of blood is collected into a heparinized syringe (to heparinize the syringe, aspirate some heparin [5,000 units/ml] into syringe, rinse the syringe and expell the excess liquid). Four ml of blood is placed in catecholamine collection tube (WHITE TOP) while 5 ml each is placed in 3 LAVENDER TOP tubes (do not use the vacuum--open the cap and gently expell the blood to prevent hemolysis).

Cap the tubes and gently invert them 3-4 times. Make sure that the white residue at the bottom of the catecholamine collection tube (WHITE TOP) is completely dissolved. Place all the tubes in ice (4°C). All the tubes are centrifuged within one hour of collection at 1,500 x g in a refrigerated centrifuge for 15 min at 4°C (e.g., Beckman J6B with JS 4.2 rotor at 2,000 RPM).

- (a) Plasma from catecholamine collection tube is placed in catecholamine storage tube (RED TOP) (see flow chart below).
- (b) Plasma from renin collection tube is placed in renin storage tube (BLUE TOP).

Transfer plasma with disposable plastic pipettes. When transferring plasma sample, do not collect the buffy coat found above the red cell layer.

All tubes are to be labelled with the following:

- (a) Code number of the patient
- (b) date of collection
- (c) center number

Cover the label with 3M magic tape to prevent the label from peeling or rubbing off in the freezer during storage. Store the samples in a  $-70^{\circ}$ C freezer in the storage box provided. (Sample should not be stored for more than one week in a  $-20^{\circ}$ C freezer.)

Central laboratory will provide, at two month intervals, a fresh lot of collection and storage tubes.

